	
For subjects who received a replacement intracanalicular depot starting at the 6 Week Visit and prior to the 12 Week Visit:
 
If the intracanalicular depot is still present in one or both eyes at the 20 Week Visit, the Investigator will attempt to remove the intracanalicular depot from the respective eye(s). If removal is successful bilaterally, the subject will be exited from the study. If removal at the 20 Week Visit is not successful in one or both eyes, the subject will be required to return to the clinic every 30 (\pm 10) days until the intracanalicular depot is confirmed to be no longer present.
 
If the intracanalicular depot is not present bilaterally at the 20 Week Visit, the subject will be exited at the end of the visit.
 
The subject may be prescribed IOP-lowering drops at the Investigator's discretion.

Statistical Methods	
Hypotheses:
 
H_0: The difference between study eyes that received OTX-TP and study eyes that received PV (OTX-TP minus PV), in mean IOP at the following time points: 8AM, 10AM, and 4PM at the 2 Week, 6 Week, and 12 Week Visits, is ≥ 0 mmHg for at least one time point over all visits.
 
H_1: The difference between study eyes that received OTX-TP and study eyes that received PV (OTX-TP minus PV), in mean IOP at the following time points: 8AM, 10AM, and 4PM at the 2 Week, 6 Week, and 12 Week Visits, is < 0 mmHg for all time points over all visits.
 
Sample Size:
 
Assuming a common standard deviation of 3.75 mmHg within a treatment group, a mean difference of 1.5 mmHg or greater between treatment groups at each of the 3 time points of each of the 3 visits, and a 3:2 randomization ratio, 294 subjects in the OTX-TP arm and 196 subjects in the PV arm yield $>90\%$ power to conclude superiority of OTX-TP to PV in mean IOP at all of the 9 time points using a 2-sided alpha = 0.05 and assuming independence among time points. The power increases with increasing positive correlation among time points.
 
To account for 10% of subjects discontinuing before the 12 Week Visit, approximately 330 subjects will be randomized into the OTX-TP arm and 220 subjects will be randomized into the PV arm.
 
Primary Analysis:

	
The primary analysis of the primary efficacy outcome will employ a linear model with IOP at the given visit (2 Week, 6 Week, and 12 Week) and time point (8AM, 10AM, and 4PM) as the response, time point specific baseline IOP as a covariate, and treatment as a main effect factor, using the intent to treat population with multiple imputation methods using Monte Carlo Markov Chain approach to impute missing data and using last time-consistent observation carried forward to impute data for time points after a subject's study eye is prescribed IOP-lowering drops. Each time point within each visit will be modeled separately. The least squares mean differences (test – control) between OTX-TP and PV will be presented along with 2-sided 95% confidence intervals (CIs) around the difference and 2-sided p-values testing the difference equal to 0. Inference will be made on the 2-sided p-value at a 2-sided alpha = 0.05 at each time point and visit.
 
The study will be considered a success if the 2-sided p-value < 0.05 and the point estimate of the difference is < 0 at all time points over the three visits.
 
Sensitivity analyses, to determine robustness of results, will be performed using multiple imputation methods with pattern mixture models, last time-consistent observation carried forward (LOCF), and baseline time-consistent observation carried forward to impute missing values and observed data only. Additionally, sensitivity analyses will be performed on the per protocol population using observed data only.

--	---

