	
Subjects not currently treated with a prostaglandin analogue will undergo a 2 week run-in starting at the Screening Visit, to confirm they are a prostaglandin responder. At least two IOP measurements will be taken over a two week period (Run-in Visit 1 at 2 days [+ 3 days] post-initiation of prostaglandin therapy; and Run-in Visit 2 at 11 days [+ 3 days] post-initiation of prostaglandin therapy). The Run-in IOP measurements will be conducted at 8 AM +/- 1 hour, to confirm the response to prostaglandin therapy. Once the response is confirmed, the subjects will undergo a 6 week (- 2 days/+ 3 days) washout period prior to Baseline Visit 1. The Baseline Visit 2/Insertion Visit, Day 1, will be conducted two to four days after the Baseline Visit 1. The IOP measurement at Baseline Visit 2 must demonstrate a \geq 5 mmHg increase from Run-in Visit 2. IOP measurements at the baseline visits will confirm that the washout period was sufficient.
 
Subjects who have exited from another ophthalmic investigational research study within the last 8 weeks will be started on a 6 week prior trial recovery period and stop all glaucoma/OHT meds, after completing Informed Consent and the Screening Visit. They will then be discussed with the Medical Monitor, in order to obtain written approval to be allowed to participate in the current study. The approval will be captured on the appropriate eCRF. Timing and requirements for the period between Screening and Baseline Visit 1 will vary, please refer to Appendix A for additional specifications.
 
At Baseline Visit 2/Insertion Visit (Day 1), if insertion is unsuccessful in one eye, the intracanalicular depot from the contralateral eye (if already inserted) will not be removed. The subject will be prescribed IOP-lowering drops at the Investigator's discretion for the eye that did not receive a depot. These subjects will be followed for safety only, and the eye that received a depot will be included in the safety analysis. The study will be supplemented with additional subjects to account for these subjects in order to ensure that the necessary number of subjects who receive a depot bilaterally are followed through the 12 Week Visit for efficacy and safety.
 
All subjects will undergo follow-up visits at 2, 4, 6, 8, 10, and 12 Weeks. If at any visit, the investigator deems it necessary to initiate IOP-lowering drops as rescue therapy due to an increase in IOP, the subject will begin the IOP-lowering drops at the Investigator's discretion and followed through the remainder of the study for safety. Sensitivity analyses, to determine robustness of results, will be performed using Monte Carlo Markov Chain approach to impute non-monotone missing

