
Screening Assessment
 
(Visit timing will vary based on randomization stratum: A, B, or C)
 
This visit may be conducted over two days, separating the IOP Measurement, Automated perimetry, and/or pachymetry only.
 
All IOP Measurements must be conducted within \pm 60 minutes of the required time, and must be conducted at approximately the same time at each of the follow-up visits.
	
 • Informed consent • Demographic data • Iris color • Medical and ophthalmic history • Medication history • Urine pregnancy test (if applicable): if female of childbearing potential, subject must utilize reliable contraceptive methods for the duration of the study as judged by the Investigator, and have a negative urine pregnancy test 
The following will be performed on both eyes:
 
 • Assessment of Best Corrected Visual Acuity (BCVA) • Automated perimetry • Pachymetry 
The average of the 3 measurements will be calculated to determine subject eligibility. Contact lens wear must be discontinued 3 days prior to pachymetry for soft contact lenses and 14 days prior to pachymetry for rigid gas permeable contact lenses. For contact lens wearers, the pachymetry assessment may be scheduled for a separate day from the Screening Visit based on the type of contact lens (i.e., 3 days after the Screening Visit for soft contact lenses and 14 days after the Screening Visit for rigid gas permeable contact lenses)
 
 • Slit lamp biomicroscopy • Assessment and grade of ocular hyperemia (at slit lamp) • Punctum exam (for normality of punctal appearance, lid apposition, and tear meniscus) • Punctum size assessment using a punctum gauging system provided by the Sponsor • IOP measurement (Goldmann applanation tonometry) at 8AM \pm60 minutes • Gonioscopy • Dilated fundus exam • Adverse event assessment 
At the end of the Screening Visit:
 
 • Subjects will be instructed to start washout, run-in, or prior trial recovery period based on prior prostaglandin therapy and/or prior participation in an ophthalmic investigational research study. Please refer to Appendix A for subjects who need to start the prior trial recovery period.
--	---

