4.5.7.1. Screening Visit

The following procedures and assessments will be completed at least 6 weeks (-2/+3 days) prior to the Baseline Visit 1 for Stratum A, at least 8 weeks (-2/+3 days) prior to Baseline Visit 1 for Stratum B, and as instructed by Medical Monitor for Stratum C, to allow for adequate washout of potential subject's current OAG/OHT medication(s):

- Obtain informed consent

- Demographic information: age, gender, ethnicity, height, weight (height and weight may be self-reported by subject)
- Iris color
- Medical and ophthalmic history
- Medication history
- Urine pregnancy test (if applicable): If female of childbearing potential, subject must utilize reliable contraceptive methods for the duration of the study as judged by the Investigator, and have a negative urine pregnancy test.

The following procedures and assessments will be performed for both eyes:

- Best Corrected Visual Acuity
- Automated perimetry
- Slit lamp biomicroscopy
- Assessment and grade of ocular hyperemia (at slit lamp)
- Punctum exam (for normality of punctal appearance, lid apposition, and tear meniscus)
- Punctum size assessment using a punctum gauging system provided by the Sponsor
- IOP measurement (Goldmann applanation tonometry) at 8AM ±60 minutes
- Pachymetry: The average of the 3 measurements will be calculated to determine subject eligibility. Contact lens wear must be discontinued 3 days prior to pachymetry for soft contact lenses and 14 days prior to pachymetry for rigid gas permeable contact lenses. For contact lens wearers, the pachymetry assessment may be scheduled for a separate day from the Screening Visit based on the type of contact lens (i.e., 3 days after the Screening Visit for soft contact lenses and 14 days for rigid gas permeable lenses).
- Gonioscopy
- Dilated fundus exam
- Adverse event assessment
- At the end of the Screening Visit:
 - Subjects will be instructed to start washout, run-in, or prior trial recovery period based on randomization stratum. Please refer to [Appendix A](#) for subjects who need to start the prior trial recovery period.

4.5.7.2. Run-in Visits 1 and 2

For subjects in Stratum B, Run-in Visit 1 will be 2 days (+ 3 days) post-initiation of prostaglandin therapy for subjects; and Run-in Visit 2 will be 11 days (+ 3 days) post-initiation of prostaglandin therapy.

The following will be performed for both eyes:

At 8AM (T₀)

- IOP measurement (Goldmann applanation tonometry)
- Adverse event assessment

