10. APPENDICES

[**Appendix A**](#) : Instructions for Determining Eligibility of Subjects Exiting From Prior Ophthalmic Investigational Research Studies

[**Appendix B**](#) : Procedures for Study Assessments

[**Appendix C**](#) : Instructions for Removal of OTX-TP or PV

APPENDIX A. INSTRUCTIONS FOR DETERMINING ELIGIBILITY OF SUBJECTS EXITING FROM PRIOR OPHTHALMIC INVESTIGATIONAL RESEARCH STUDIES

Please refer to the table below for determining eligibility and Visit Schedule for subjects who have exited an ophthalmic investigational research studies within 8 weeks of the Screening Visit. Please consult the Medical Monitor (MM) after obtaining informed consent. Written approval from the Medical Monitor will be required for the subject to continue in the Study after the Screening Visit.

Subject has just exited a study for any ophthalmic indication and may be interested in the Ocular Therapeutix (OTX) investigational research study
 
→ Complete Informed Consent and Screening Visit for OTX investigational research study
 
→ Begin 6 week prior trial recovery period and stop all glaucoma/ocular hypertension (OHT) medications
			
Was this an investigational research study for ocular anti-hypertensive therapy?			

YES: was subject stable and IOP controlled on ocular anti-hypertensive medication for 8 weeks prior to start of non-OTX ophthalmic investigational research study?
		
NO: i.e., investigational research study was for another ocular indication that is not excluded by protocol. Was subject stable and IOP controlled on ocular anti-hypertensive medication for 8 weeks prior to start of non-OTX ophthalmic investigational research study?
	
Is there history of monotherapy with a Prostaglandin Analogue (PGA) and a response?		Is there history of monotherapy with a Prostaglandin Analogue (PGA) and a response?*	

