
YES: was there a 5 mm Hg or greater increase in IOP after PGA washout prior to or during non-OTX ophthalmic investigational research study? Documentation of Med History confirmed by MM?
 
→ If Yes: Proceed to IOP Confirmation Visit at the end of the 6 week prior trial recovery period. (8 AM IOP must be ≥ 24 and ≤ 34 mm Hg).
 
→ If Yes: return in 2 weeks for Baseline Visit 1. (Stratum C).
 
If No: Screen Failure
		
NO: is subject PGA naïve or on therapy with a PGA plus a second agent at time of entry to non-OTX ophthalmic investigational research study?
 
→ If Yes: At the end of the 6 week prior trial recovery period, perform IOP Confirmation Visit and start 2 week run-in period with PGA. If adequate response at Run-in Visits 1 and 2, then 6-week washout period and proceed to Baseline Visit 1 (Stratum B).
 
If No: Screen Failure.
	

YES: was there a 5 mm Hg or greater increase in IOP after PGA washout prior to or during non-OTX ophthalmic investigational research study? Documentation of Med History confirmed by MM?
 
→ If Yes: Proceed to IOP Confirmation Visit at the end of the 6 week prior trial recovery period. (8 AM IOP must be ≥ 24 and ≤ 34 mm Hg).
 
→ If Yes: return in 2 weeks for Baseline Visit 1. (Stratum C).
 
If No: Screen Failure
		
NO: is subject PGA naïve or on therapy with a PGA plus a second agent at time of entry to prior non-OTX ophthalmic investigational research study?
 
→ If Yes: At the end of the 6 week prior trial recovery period, perform the IOP Confirmation Visit and start 2 week run-in period with PGA. If adequate response at Run-in Visits 1 and 2 is demonstrated, then start 6-week washout period and proceed to Baseline Visit 1 (Stratum B).
 
If No: Screen Failure.
	

*If subject is exiting a prior non-OTX ophthalmic investigational research study for an allowed indication other than ocular anti-hypertensive therapy and has continued PGA monotherapy during the study, subject (again, with Medical Monitor approval) should discontinue PGA therapy and proceed to Baseline Visit 1 at the end of the 6 week prior trial recovery period (Stratum A).

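### Prior-trial entrants on glaucoma drops can be taken off them before the Medical Monitor has reviewed history that may rule them out (minor; wording fix)

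*Protocol*

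**What the plan says.** The Synopsis (Study Design) and Section 3.5 give one sequence for subjects who left another ophthalmic study within 8 weeks: consent and Screening, then the start of a 6 week recovery period with all glaucoma and ocular hypertension drugs stopped, and after that "They will then be discussed with the Medical Monitor, in order to obtain written approval to be allowed to participate in the current study".

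Other places bear on the same step:

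- The Appendix A flow box puts the instruction to "stop all glaucoma/ocular hypertension (OHT) medications" in its opening step, above the history questions.
- The Synopsis (Screening Assessment) acts at the end of the Screening Visit: "Subjects will be instructed to start washout, run-in, or prior trial recovery period based on prior prostaglandin therapy". Section 4.5.7.1 does the same, with a different basis: "Subjects will be instructed to start washout, run-in, or prior trial recovery period based on randomization stratum".
- The note to Exclusion Criterion 3 (Synopsis and Section 4.4.2) has Stratum C subjects stop non-prostaglandin ophthalmic drugs at Screening and begin recovery.
- The Appendix A introduction says "Please consult the Medical Monitor (MM) after obtaining informed consent" and "Written approval from the Medical Monitor will be required for the subject to continue in the Study after the Screening Visit".
- The Appendix A footnote covers subjects who stayed on prostaglandin monotherapy in a trial for another indication: the "subject (again, with Medical Monitor approval) should discontinue PGA therapy".

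**The concern.** Some of what the Medical Monitor reviews is history. One Appendix A branch asks, for example, "Documentation of Med History confirmed by MM". Where the history is unsuitable the subject is a screen failure, and no pressure reading off treatment is needed to establish that. If drops are stopped first, a subject who was never going to qualify spends time untreated for no trial purpose.

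This is a participant-protection point. Treatment assignment, the nine-time-point primary analysis, power and type I error do not depend on it.

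**Working it through.** The plan states no figure on this point, so the check sets the texts side by side and adds arithmetic on the visit windows.

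**1. Order of events.** The Synopsis and Section 3.5 are explicit: stop, then consult. The Criterion 3 note, the end-of-Screening instructions and the flow box are consistent with that order. The Appendix A introduction permits approval before stopping but does not say that drops continue until approval is given, and it sets no deadline for the review. Only the footnote ties stopping to approval, and only for its own subgroup.

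**2. Can a refusal rest on records alone?**

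- Appendix A: no history of response to prostaglandin monotherapy and, at entry to the prior study, neither prostaglandin-naive nor on a prostaglandin plus a second agent. This ends in screen failure and needs only past records.
- Inclusion Criterion 3 note: the Medical Monitor's review must establish 8 weeks of stable treatment (or no treatment) before the prior trial. This too is a matter of record.
- Appendix A: a monotherapy responder with no documented rise of 5 mmHg after an earlier washout. This is also history, but less clear-cut. The screen-failure line in that cell follows the IOP Confirmation step, and the Criterion 3 note sends subjects without a documented response to a run-in.

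Failures on the IOP Confirmation result (8 AM IOP outside 24 to 34 mmHg) or on run-in response need readings from this study. They are outside the point.

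**3. Who is exposed?** A prior-trial entrant who is on drops at Screening, is outside the footnote subgroup, is not already excluded by the investigator at Screening, and is then refused on history. The documents do not say how many there are.

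**4. Time off drops.** Let t be the Medical Monitor's turnaround after the stop and r the time from refusal to restart.

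- Stop first: needless time = t + r.
- Approval first: needless time = 0.

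The documents give neither t nor r. Assuming t = 0 to 14 days (an assumption with no source in the documents), the result is 0 + r to 14 + r days.

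The first scheduled pressure check after stopping is the IOP Confirmation Visit (Section 4.5.7.3), at 42 − 2 = 40 to 42 + 5 = 47 days. Section 4.5.3 requires no further visits for screen failures and does not mention restarting therapy.

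**5. Effect on timing if approval comes first.** Recovery starts t days later.

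- Section 4.5.7.3 ties the confirmation visit to the end of recovery, so it moves with the stop date.
- Section 4.5.7.1 leaves the Stratum C interval from Screening to Baseline Visit 1 to the Medical Monitor.
- For Stratum B, Appendix A already implies 6 + 2 + 6 = 14 weeks, against the 8 weeks in Section 4.5.5. The general interval therefore does not describe these subjects even now.
- Prior-trial entrants reach Stratum A through the footnote. Its window is 42 − 2 = 40 to 42 + 3 = 45 days after Screening. With at least 40 days off drops, 45 − 40 = 5 days of turnaround fit. Stopping is already tied to approval there, so the fix adds no new delay.

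**The case against.** The strongest reply is that a gate already exists. The Synopsis and Section 3.5 defer to Appendix A, which asks for consultation after consent and requires written approval to go on after Screening. Recovery is a step after Screening, so a careful site can hold approval before any drop is stopped. Screening may also be split over two days for certain tests. On this view the text is loosely drafted and does not plan an unapproved washout. That stands in part: early approval is allowed. It is not required, the flow box beneath that introduction lists the stop first, and two other sections state the opposite order outright.

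A second reply is that few subjects are affected. Known poor responders fall under Exclusion Criterion 1 and can be failed at Screening. Subjects who were prostaglandin-naive or on two agents at prior-study entry go to a run-in. Subjects on no drops have nothing to stop. All of this stands and makes the group narrow, but it does not empty it, because the first two routes in step 2 of the working remain.

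A third reply is that restarting treatment after refusal is ordinary care. Principal Investigators are ophthalmologists experienced in glaucoma, and the ban on other hypotensive drugs applies only during the study. That stands, so the missing restart instruction is not counted as a defect. Rescue drops (Sections 3.5 and 4.7.2) also limit the risk. They are triggered by high or uncontrolled pressure, not by refusal, so they do not prevent a needless interruption.

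**Conclusion.** The point holds as a minor one. For prior-trial entrants still on drops, the protocol's explicit order is to stop first and review afterwards, although part of the review can refuse a subject on records alone. The needless time off treatment is the turnaround plus restart time. Its range of 0 to 14 days plus restart rests wholly on the assumed turnaround, and its lower end is no harm apart from the restart time. The group is narrow and of unknown size.

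Three stronger readings are not supported:

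- **That an ineligible subject is planned to go untreated until the confirmation visit at day 40 to 47.** Appendix A requires written approval to continue after Screening, so reaching that visit unapproved would be a deviation.
- **That refused subjects are left without therapy.** Section 4.5.3 is silent on this for every screen failure, and nothing bars the investigator from resuming treatment.
- **That the visit intervals and the SAP must be rewritten.** Sections 4.5.7.1 and 4.5.7.3 already let timing follow the stop date for the groups that matter.

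**What to change.** In the Synopsis (Study Design, Exclusion Criterion 3 note and Screening Assessment), Section 3.5, the Exclusion Criterion 3 note in Section 4.4.2, Section 4.5.7.1 and the Appendix A flow box, state two things: prior-trial entrants remain on their current drops until the Medical Monitor approves in writing, and the 6 week recovery period starts on the day the drops are stopped. The Criterion 3 note must be included in both places, or its stop-at-Screening wording would contradict the new order.

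The cost is protocol wording only. The downside is that recovery starts later by the Medical Monitor's turnaround, which the documents do not give. No SAP change is needed.

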3. INTRODUCTION

Ocular Therapeutix, Inc. (OTX) is a biopharmaceutical company focused on developing medical device and drug products to address unmet and underserved medical needs in ophthalmology. OTX was founded to further develop its proprietary polyethylene glycol (PEG) hydrogel technology in various ophthalmic applications. Ocular Therapeutix has designed a bioabsorbable intracanalicular depot as the platform for drug delivery products, which can be used to deliver various active pharmaceutical ingredients that have been included in other FDA-approved drug products. The intracanalicular depot is designed to be inserted into the inferior or superior punctum and then be retained in the canaliculus for the entire duration in which the drug is being delivered. Over this time and through hydrolysis, the intracanalicular depot softens, liquefies and is cleared through the nasolacrimal duct. Another similar hydrogel product, ReSure Sealant, manufactured by Ocular Therapeutix was FDA approved for ophthalmic use (reference PMA P130004) on January 8, 2014.

